7.1 Procedure Schedules – Full Protocol

SCI and Controls – Complete protocol

PROCEDURE	7.2 INITIAL EVALUATION			7.3 AIM 1	7.4 AIM 2
	Visit #1 Functional Mapping	Visit #2 Range of Motion	Visit #3 Familiarization	Visit #4 TMS	Visit #5 StartReact
Kinematic recordings					
EMG recordings					
Transcutaneous SCS					
BoMI					
Motor tasks					
TMS					
StartReact					

7.2 Initial evaluation: Determine the effect of SCS on motor responses and range of motion

To determine an initial baseline for each participant, we will evaluate motor responses elicited by transcutaneous SCS in the initial evaluation phase. Participants will visit the lab for 1) a functional mapping where we measure spinal responses elicited by SCS, 2) a range of motion evaluation where we measure the range of motion on different joints with and without SCS, and 3) a familiarization phase where participants learn to control the body-machine interface using their leg movements supported by SCS.

Participants: 100 unimpaired participants and 12 participants with spinal cord injury (spinal cord injury level C4-T9) with motor impairments in the legs (complete ASIA A, or incomplete ASIA B, C, or D) and in the chronic stage of SCI (>6 months postinjury) will participate in this experiment, which will be submitted for review and approval to Washington University School of Medicine Institutional Review Board. Unimpaired participants will be recruited to perform either one of the five potential visits (Visits# 1-5) or all five visits. Approximately 16 unimpaired participants are expected to complete each type of protocol. SCI participants will be recruited for the five visits in total.

Experiments with unimpaired, control participants will be used to refine collection procedures and instruments and to prepare an improved, more refined research design that will ensure effective and high-quality data collection with SCI participants. Data collected on control subjects will also be used to establish baseline behavior for comparison of SCI participant task performance and may be used to generate generalizable knowledge.

Kinematic recordings: Kinematic recordings will be obtained at a 100 Hz sampling rate using a 3D markerless motion capture system (Miquis-Hybrid, Qualisys, Sweden) consisting of 10 HD cameras covering the entire workspace. Head, trunk, and bilateral upper and lower extremity kinematics will be captured by these 2MP cameras or by infrared cameras and positioning virtual markers over standardized anatomical landmarks.

Muscle activity recordings (EMG): Muscle activity (EMG) will be acquired bilaterally at 1 kHz

using a 16-channel wireless system (Trigno Avanti, Delsys, Natick, MA). The area around muscles will be shaved and cleaned with an abrasive cream and alcohol. Bipolar surface electrodes will be placed over the form of the iliopsoas, rectus femoris, vastus lateralis, semitendinosus, biceps femoris, tibialis anterior, medial gastrocnemius, and soleus muscles. Prior to electrode placement, the area around each muscle will be shaved and cleaned with an abrasive cream and alcohol. EMG signals will be processed according to the SENIAM (Surface Electromyography for the Non-Invasive Assessment of Muscles) standards for EMG recordings and band-passed filtered between 10 and 450 Hz using a 4th order Butterworth filter. A moving average of the rectified EMG signal within a centered 250 ms time window will be used to generate normalized EMG envelopes for quantification.

Transcutaneous spinal cord stimulation (SCS): During the stimulation phases of the study, non-invasive transcutaneous electrical stimulation will be delivered to the lumbar segments of the spinal cord below the injury using a DSR8 biphasic constant-current stimulator (Digitimer, UK) with a range of 0-1,000 mA. Stimulation will be administered using two pairs of conductive self-adhesive electrodes with a diameter of 3.2 cm placed on the skin over the spinal midline between the spinous processes of the L4 and L5 vertebrae to act as cathodes. The center of the cathodes will be located ~2 cm left and right of the midline. Two additional 5x10 cm electrodes will be placed symmetrically on the skin over the abdomen to be used as anodes^{56,57}. The stimulation waveform will be biphasic, rectangular, with 1 ms pulses at a frequency of 1-100 Hz. As an additional alternative, the stimulation will be filled with a carrier frequency of 5 KHz. It is thought that a 5-10 KHz carrier frequency is beneficial for improving muscle strength⁵⁸ and for suppressing the sensitivity of pain receptors⁵⁹, and is therefore more comfortable for human participants^{11,60,61}.

Functional mapping: Recordings will be performed with single-pulse, graded stimulation amplitudes as subjects lay supine on a table in order to compute the degree of recruitment of each muscle with increasing stimulation amplitudes as previously described in my work⁷.

Range of motion: Kinematic recordings will be performed to quantify the range of motion at the different joints with and without transcutaneous SCS.

Body-machine interface: Participants will be fitted with a body-machine interface to control a computer cursor using the legs. Leg movements will be recorded using non-invasive, wireless inertial measurement unit (IMU) motion sensors (YostLabs, Portsmouth, OH) attached with Velcro® to adjustable straps around the legs or with double-sided skin tape. User-specific body motions will be decoded and converted into the two coordinates of the cursor in real-time as previously described in my work⁶².

Familiarization: Participants will have the opportunity to familiarize themselves with the control of the BoMI using SCS and perform different types of game-like activities like center-out reaching, pong, solitaire, Tetris, and other flash games, as well as the motor tasks (described below).

7.1 Aim 1: Determine which kinds of SCS-enabled movements are mediated by the corticospinal tract

An increasing number of studies supports the view that SCS can restore posture, stepping, and voluntary walking in humans with SCI^{4,7,17}. The prevailing view is that by elevating the functional state of spared spinal sensory-motor networks below the lesion, residual descending pathways can transmit activity that enables and amplifies voluntary motor control¹⁵. Although epidural SCS can enable force production in paralyzed muscles⁷, whether motor improvements are mediated by the corticospinal tract or the reticulospinal remains unknown.

In a 45-min session, we will deliver non-invasive transcutaneous SCS to the lumbosacral enlargement as participants use their SCS-facilitated leg movements to control a non-invasive body-machine interface (BoMI) on a computer screen and perform game-like activities^{62,63}. To determine which kinds of SCS-enabled movements are mediated by corticospinal networks, participants will perform two motor tasks before and after training requiring different degrees of dexterity: precision control vs. maximum range of motion; using two types of movements: hip vs. ankle flexion. To quantify changes in neural excitability of the corticospinal tract, we will compare motor-evoked potentials (MEPs) elicited by transcranial magnetic stimulation of the leg motor cortex⁶⁴ as participants perform the motor tasks. We postulate that MEP responses will be enhanced for the precision-control task in distal muscles (tibialis anterior), which are thought to require a high involvement from the corticospinal tract. *Our hypothesis is that SCS will further enhance the MEP response for these movements, but not for range-of-motion movements, or movements with proximal muscles (rectus femoris).*

Transcranial magnetic stimulation (TMS): Motor evoked potentials (MEPs) in the tibialis anterior and rectus femoris muscles will be evoked by TMS of the contralateral motor cortical leg area using a Magstim 200² stimulator (Magstim, UK) through a double cone coil and a monophasic current waveform delivered at 4-s intervals. The motor threshold for both muscles will be identified⁶⁵ and that intensity will be used to elicit and average twenty MEPs at each timepoint²⁴. Average MEP response amplitude will be used to quantify changes in corticospinal tract excitability¹⁵. If no motor threshold is detected at 100% device stimulation intensity due to SCI (and interrupted circuits), the 100% stimulation intensity or the maximum tolerable intensity will be used. MEP responses will be measured during rest and during an active contraction (Motor Tasks, see below) before and after BoMI training, as well as with and without SCS. To estimate changes in MEPs, response amplitudes under different conditions will be normalized to the baseline (before training, resting) response.

Motor tasks: Immediately before after the BoMI session, participants will wear a VR headset (Oculus Quest 2, Facebook, CA) to block their view. The IMUs on the legs will measure and digitize their leg joint angles. A real-time virtual representation of one of their joint angles will be presented through the VR. Participants will be asked to perform two tasks requiring different types of motor control. In the range-of-motion task, participants will be instructed to flex or extend their legs to surpass a virtual target of a specified amplitude. In the precision-control task, participants will have to move their joint and hold the position within a target range of a specified amplitude for 1 second. We will examine motor-evoked potentials elicited by TMS (*Aim 1*) and the StartReact response (*Aim 2*) as individuals perform the task under two conditions: with SCS and without SCS using the knee and ankle joints. As an alternative to the VR headset, a wall projector will be used to perform the motor tasks.

BoMI Training: Participants will perform visuo-spatial motor tasks over a 45min session with SCS. The tasks will consist of different types of game-like activities like center-out reaching, pong, solitaire, Tetris, and other flash games.

Expected outcomes, potential problems, and alternative strategies: Based on previous studies by other groups, it is our expectation that MEP responses will be enhanced for the precision-control task in distal muscles (tibialis anterior), which are thought to require a high involvement from the corticospinal tract. *We hypothesize that SCS will further enhance the MEP response for these movements, but not for range-of-motion movements, or movements with proximal muscles (rectus femoris).*

The main challenge in this study will be the recruitment of a sufficiently large group of volunteers with spinal cord injuries in the C4-T9 level. If this will not be feasible, we will extend the study to individuals with lesions at the C2-C3 level that have complete or partial paralysis in the legs. Furthermore, we can seek to further extend the study to other hospitals in the St. Louis region like the Barnes Jewish Hospital, the Rehabilitation Institute of St. Louis, SSM Rehabilitation Hospital, and the VA Medical Center Spinal Cord Injury Program. Another potential difficulty may arise because of the high expected attrition with severely disabled volunteers. As a consequence, some evaluations might be interrupted. To preserve uniformity of statistical power across the study, we will retain the results of participants with an incomplete number of sessions in separate data sets. The analysis of incomplete data sets will take explicitly into account the causes for abandoning the study (e.g. dissatisfaction with the methodology, change in medical condition, etc).

Our approach will have –by design an objective—a degree of customization based on each individual’s specific mobility and potential for movement restoration with SCS. Therefore, there might be a small initial difference in performance. However, our previous studies have demonstrated an improvement in performance with training independent of differences in the BoMI map between subjects^{22,62,66,67}.

One possibility is that 45 minutes of BoMI training is not sufficient to observe changes in corticospinal and reticulospinal tract excitability within a single session. If this is the case, we will increase the duration of BoMI training to 2 hours. Twenty minutes to 2 hours of SCS and motor training have been shown to be sufficient to observe changes in motor function^{61,68,69} as well as spinal¹⁵, cortical²⁴, and subcortical¹¹ excitability in human subjects.

Support of limb weight may introduce a force production confound when participants have to generate torque to move their foot compared to their whole leg. If this is the case, we will perform the motor task evaluations as participants lay on their side as manual support is provided to counter the effects of gravity.

7.2 Aim 2: Determine which kinds of SCS-enabled movements are mediated by the reticulospinal tract

Using the same protocol as Aim 1, we will test whether SCS can enhance the StartReact response time and amplitude. To quantify changes in neural excitability of the reticulospinal tract, we will compare the StartReact response⁷⁰ (a shortening in response time after a startling auditory stimulus) as participants perform the motor tasks before and after BoMI training.

StartReact response: Participants will be instructed to reach the target as fast as possible after it is presented. Response time will be identified from EMG activity⁷¹ and measured when the target is presented alone (visual reaction time), when it is paired with a soft auditory stimulus (80 dB, 500 Hz, 50 ms, visual-auditory reaction time), or with a startling acoustic stimulus (120 dB, 500Hz, 50ms, visual-startle react time) presented through audio speakers (T-15, Polk Audio). To quantify changes in StartReact responses, response times under different conditions will be normalized to the baseline response.

Expected outcomes: Based on previous studies by other groups^{47,71,72}, I expect the StartReact response time to be the shortest for the startle response, where the reticulospinal tract is engaged. Furthermore, I expect that SCS will have an additional enhancement of this response, but only for tasks that require a high involvement from the reticulospinal tract. *We hypothesize that SCS will enhance the StartReact response for the range-of-motion task in proximal muscles (rectus femoris), but not for precision-control movements, or movements with distal muscles (tibialis anterior).*

8. Data Analysis and Statistical Plan

Average MEP and StartReact responses (of 20 responses) will be used to quantify changes in corticospinal and reticulospinal tract excitability¹⁵. A paired sample t-test of response amplitude and latency (time from stimulation to muscle response) will be used to test the hypothesis that BoMI training with SCS results in enhanced corticospinal tract excitability during precision-control movements and reticulospinal tract excitability during range-of-motion movements. In addition, a Student's *t*-test with a Holm-Sidak adjustment for multiple comparisons will be performed to compare the difference between changes in corticospinal excitability induced by the type of motor task (precision control vs. range-of-motion), joint (ankle vs. hip), and group (control vs. SCI).

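### A fixed 4-s TMS interval can lock to the SCS pulse train, leaving one uncontrolled lag per SCS-on block that averaging 20 MEPs would not remove

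*Combined protocol and SAP*

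**What the plan says.** The TMS paragraph under Aim 1 (section 7) specifies stimulation "through a double cone coil and a monophasic current waveform delivered at 4-s intervals". At the threshold intensity, "that intensity will be used to elicit and average twenty MEPs at each timepoint", and the mean amplitude is the outcome: "Average MEP response amplitude will be used to quantify changes in corticospinal tract excitability". MEPs are taken at rest and during the motor tasks, "before and after BoMI training, as well as with and without SCS".

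The SCS paragraph under the initial evaluation (section 7.2) gives the other pulse train: "The stimulation waveform will be biphasic, rectangular, with 1 ms pulses at a frequency of 1-100 Hz". A carrier is optional: "As an additional alternative, the stimulation will be filled with a carrier frequency of 5 KHz". The rate to be used in the MEP blocks is not stated.

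Section 8 analyses amplitude and latency with paired t-tests and has no term for the time between an SCS pulse and a TMS pulse. None of these sections gives a trigger link, a lag, a jitter of the TMS interval, or a record of SCS pulse times.

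**The concern.** Two periodic stimuli are delivered together. If the TMS interval is an exact multiple of the SCS period, every TMS pulse in a block lands at the same point of the SCS cycle. That point is set by chance when the block starts and may differ in the next block. For this one source of variation, the twenty MEPs then amount to a single observation.

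The documents give two reasons why the lag could matter. Functional mapping at Visit 1 uses single SCS pulses to "compute the degree of recruitment of each muscle with increasing stimulation amplitudes", so SCS pulses can drive the recorded muscles. Section 9.4 sets the SCS amplitude at either paresthesia or a motor response, so in some participants an SCS-evoked response, or its artefact, could fall inside the MEP window. With a locked lag it would fall at the same place in all twenty sweeps and survive averaging. Latency could be affected as well as amplitude.

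At stake is precision in comparisons that involve an SCS-on block, with 12 SCI participants.

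**Working it through.** The plan states no figure for SCS-to-TMS timing, so there is none to reproduce.

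**1. Does the interval lock?** The phase advance per TMS pulse is (4 × f) mod 1, where f is the SCS rate in Hz.
- Whole-number f from 1 to 100: the advance is 0 at all 100 rates.
- Multiples of 0.25 Hz from 1 to 100: the advance is 0 at all 397 rates.
- Carrier: 4 × 5,000 = 20,000 whole cycles, so the advance is 0.
- At 30.1, 15.2 or 33.3 Hz, the 20 pulses fall on five phases instead of one.

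**2. How fragile is the lock?** Let R be the length of the mean phase vector over 20 pulses. R = 1 is full locking, and about 0.20 is what 20 random phases give. The first-to-last span is 19 × 4 = 76 s. The mismatch and jitter values are assumed.

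| Disturbance | 15 Hz | 30 Hz | 50 Hz | 100 Hz |
|---|---|---|---|---|
| Clock mismatch 50 ppm (3.8 ms over 76 s) | 0.99 | 0.98 | 0.94 | 0.76 |
| Clock mismatch 500 ppm | 0.51 | 0.16 | 0.00 | 0.00 |
| Trigger jitter, SD 1 ms | 1.00 | 0.98 | 0.95 | 0.83 |
| Trigger jitter, SD 5 ms | 0.90 | 0.66 | 0.34 | 0.20 |
| Trigger jitter, SD 10 ms | 0.66 | 0.25 | 0.20 | 0.20 |

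Machine-timed pulses stay largely locked. Jitter of 5-10 ms largely breaks the lock at 30-100 Hz.

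**3. What does a locked lag add?** Assume a sinusoidal phase effect of amplitude A, as a fraction of MEP size. The SD it adds to a block mean is A/√2 if locked and A/√40 if the 20 phases are random, a ratio of √20 = 4.5. For A = 10%, 20%, 30% and 40%, that is 7.1%, 14.1%, 21.2% and 28.3% locked, against 1.6%, 3.2%, 4.7% and 6.3% spread.

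**4. Effect on the detectable change.** Assume a paired-change SD of 30% from all other sources, n = 12, two-sided 5% and 80% power. The noncentral t gives a detectable change of 0.889 × SD.
- Both blocks SCS-on: SD = √(0.09 + A²) locked, √(0.09 + A²/20) spread.
- One block SCS-on: SD = √(0.09 + A²/2) locked, √(0.09 + A²/40) spread.

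| A | Both on: locked / spread | One on: locked / spread |
|---|---|---|
| 10% | 28.1% / 26.7% | 27.4% / 26.7% |
| 20% | 32.0% / 27.0% | 29.5% / 26.8% |
| 30% | 37.7% / 27.3% | 32.7% / 27.0% |
| 40% | 44.4% / 27.8% | 36.6% / 27.2% |

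**5. Does the remedy work?** With intervals of 4 s plus a uniform random 0-1 s, simulated R is 0.20 at 1, 15, 30, 50 and 100 Hz and 0.19 at 1.5 Hz, which is the random level.

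**The case against.** The strongest reply is that locking is a possibility and not a stated feature of the plan. It needs a whole-number or quarter-hertz rate, SCS unbroken through the block, and spacing that holds to a few milliseconds. The documents fix none of these. The Aim 1 hypothesis concerns the task blocks, where a trial means passing a target or, in the precision task, having to "hold the position within a target range of a specified amplitude for 1 second". How a 4-s train fits such trials is not described, and section 9.4 calls the experiments self-paced. If pulses follow the trials, the lock probably breaks. This stands, and it limits the point mainly to resting blocks. It does not dispose of it: the 4-s rule is written without exempting task blocks, the self-pacing remark sits under motion sensors, and accidental jitter could differ between rest and the two tasks.

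A reader might also infer that every SCS pulse recruits the recorded muscles. The documents do not support that. The mapping uses graded single pulses in supine participants, and section 9.4 allows SCS at paresthesia level, where there may be no motor response.

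Finally, a lag set by chance in each block is independent across participants. It enters the observed SD, the paired t-test remains valid, and only precision is lost. This also stands.

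**Conclusion.** The point holds as a conditional one about precision. The plan fixes a TMS interval that, on stable clocks with continuous SCS at a whole-number or quarter-hertz rate, gives all 20 MEPs in an SCS-on block one chance lag. It neither controls nor records that lag. If MEP amplitude depends on it, or if an SCS response or artefact falls in the MEP window, more pulses do not help.

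A reader might infer three stronger things: that every SCS-on block is certainly locked, that the training or SCS effect is biased, or that the trial shrinks to about 5 effective participants. The first goes beyond what the documents fix. The second fails because the lag varies by chance; a single block pair can mislead, but the group mean is not shifted. The third is the extreme corner of the assumed range: A = 40% with both blocks SCS-on gives 12 × 0.098/0.25 = 4.7. At A = 10% the same formula gives 12 × 0.0905/0.10 = 10.9, and with one block SCS-on the range is 11.4 down to 6.6.

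The size therefore rests wholly on the assumed A, its sinusoidal shape and the 30% SD. The loss runs from negligible to substantial, and the documents cannot say where in that range it lies.

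**What to change.** In the TMS paragraph under Aim 1, replace the fixed interval with 4 s plus a random 0-1 s, which spans at least one full SCS cycle at any rate of 1 Hz or more. Alternatively, trigger TMS at one stated lag from the SCS pulse in every SCS-on block; this removes the noise too, but the result then applies to that lag only. Use the same interval rule in SCS-off blocks so that the conditions differ only in SCS. Record SCS pulse times alongside the 1 kHz EMG, so that the lag is known to about 1 ms and can be examined. State how TMS pulses are timed within task trials.

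The cost is a trigger or script setting. The random option adds on average 20 × 0.5 = 10 s to an 80-s block. If there are 20 blocks (rest plus two tasks at two joints, before and after training, SCS on and off), that is 200 s, a little over 3 minutes in a visit planned at 1-2 hours.

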To better understand SCS-mediated neurorecovery, studies in rodent models of SCI using viral tracing¹³ and optogenetics¹⁴ suggest that corticospinal and reticulospinal projections mediate the voluntary control of paralyzed areas enabled by SCS, and activity-dependent reorganization of these circuits may be a primary contribution towards the restoration of function that has been observed in humans⁷⁻⁹. While direct recordings of these neural structures through viral tracing and optogenetics are not currently possible in humans, experimental paradigms exist to evaluate their involvement and contribution during SCS and motor tasks^{11,15}. Twenty minutes of SCS during rest has an excitatory effect at subcortical, but not cortical levels¹¹. However, it remains unclear whether this excitatory effect can be further enhanced by combining SCS with active voluntary movement. Indeed, despite the motor-enabling effects of SCS having been first observed half a century ago¹⁶, a major breakthrough in SCI research came from the combination of SCS with activity-based training^{4,5,7-9,17}. Moreover, while SCS can immediately enable a broad range of behaviors in animal models of paralysis^{13,18-20}, independent stepping without stimulation in humans has only been observed after more than a year of intense rehabilitation with SCS^{8,9,21}. In this work, we will evaluate corticospinal and reticulospinal tract excitability via transcranial magnetic stimulation (TMS) and reaction to a loud auditory stimuli (StartReact) respectively. Having a clear understanding of the neural mechanisms that are enhanced by SCS can allow the development of therapies that directly target the excitability and plasticity states of these structures towards improved and accelerated recovery.

3. Background and Significance

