9.4 Procedures to minimize potential risks

This study will be conducted at Washington University under the supervision of the PI. The PI is trained and well-experienced in performing human subject research. Study subjects will be monitored throughout the experiment by a co-investigator. Inclusion and exclusion criteria and monitoring are designed to ensure that the risks are minimal. Subjects are informed that participation is voluntary, and they may refuse to participate and may withdraw from the study at any time without penalty.

The responses to the Beck Depression Inventory questionnaire will be reviewed in real time by team members. If, based on the questionnaires, a participant is suspected of having suicidal intent, the PI will be notified immediately and referrals will be made as needed for further evaluation.

Study staff complete training in HIPPA regulations and do not divulge confidential information regarding participants. Participant records are kept confidential with paper records in a secure location and computer records password-protected, available only to the study staff, and with subject identifiers removed.

Use of motion sensors. To avoid fatigue, experiments will be self-paced by the subject. Subjects will be instructed that they may ask to have the procedure stopped if they have any discomfort or other concerns.

Muscle activity sensors (EMG). Washing the electrode gel from the skin surface and applying unscented skin lotion after the experiments will be applied to minimize skin irritation. Shaving cream will be used to reduce the likelihood of lacerations. In case of lacerations, first aid will be applied as necessary and the EMG application will be discontinued in that area.

Transcutaneous spinal cord and peripheral nerve stimulation. Stimulation will always start at a minimum amplitude and slowly increased as subjects are instructed to give feedback on their comfort levels. Amplitudes will be chosen as the level at which a subject feels paresthesia (tingling sensation) or a motor response is elicited. These amplitudes are normally way below pain thresholds. If a subject feels discomfort at a certain stimulation amplitude, the amplitude will be lowered to a comfortable level, or stopped.

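### A larger MEP with SCS on, or after SCS training, does not by itself separate corticospinal from spinal facilitation, and SCS-on sweeps may also contain SCS-evoked EMG

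*Combined protocol and SAP*

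**What the plan says.** **Measure.** The TMS paragraph of Aim 1 (Section 7) states: "Average MEP response amplitude will be used to quantify changes in corticospinal tract excitability". MEPs are taken at rest and during the motor tasks, "before and after BoMI training, as well as with and without SCS", and are "normalized to the baseline (before training, resting) response". The hypothesis is that "SCS will further enhance the MEP response for these movements, but not for range-of-motion movements", and not for the proximal muscle (rectus femoris) either.

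**Where SCS acts.** The Introduction (Section 2) reports: "Twenty minutes of SCS during rest has an excitatory effect at subcortical, but not cortical levels". The background to Aim 1 gives the prevailing view that SCS works "by elevating the functional state of spared spinal sensory-motor networks below the lesion", so that spared descending pathways can then drive movement. The expected-outcomes text for Aim 1 cites changes in spinal, cortical and subcortical excitability after 20 minutes to 2 hours of SCS and motor training.

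**Direct muscle responses.** Functional mapping at Visit 1 uses single SCS pulses to "compute the degree of recruitment of each muscle with increasing stimulation amplitudes". Tibialis anterior and rectus femoris, the two MEP muscles, are among those recorded. SCS runs at 1-100 Hz. On its level, Section 9.4 says: "Amplitudes will be chosen as the level at which a subject feels paresthesia (tingling sensation) or a motor response is elicited".

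**Analysis.** Section 8 plans paired t-tests of amplitude and latency for the effect of BoMI training with SCS, then Holm-Sidak-adjusted comparisons by task, joint and group. It does not say whether SCS is on or off when the tested MEPs are recorded.

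**The concern.** Aim 1 asks which SCS-facilitated movements are carried by the corticospinal tract. A leg MEP reaches the muscle through the spinal circuitry that, on the protocol's account, SCS makes more excitable. A spinal effect with no corticospinal change can therefore also raise the MEP, both with SCS on and as an after-effect of training.

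There is a second route with SCS on. If the level in use elicits a motor response, the SCS-evoked EMG can fall inside the MEP window and change the measured amplitude or latency. In Aim 2, response time is read from EMG, so the same activity could be taken as response onset.

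The risk is that a spinal effect, or a recording overlap, is reported as a tract finding and carried into the clinical trial that this study is meant to prepare.

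**Working it through.** The plan states no figure on this point, so there is none to reproduce. The check has four steps.

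**1. Is there a safeguard in the text?** The Visit 4 and 5 descriptions (Aims 1 and 2) and Section 8 contain no SCS-only sweep, no subtraction, no stated timing of TMS relative to the SCS pulse, no spinal or subcortical probe and no matching of background EMG. Spinal responses are described only for Visit 1, with the participant supine. The marks in the visit table could not be read in the text used here, but its procedure list has no row for a spinal response. The potential-problems text covers recruitment, attrition, customisation, training length and limb weight, but not this. Normalisation is to the resting pre-training MEP, which does not adjust for spinal excitability.

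**2. Would an SCS pulse fall in the MEP window?** Expected pulses per window = SCS frequency × window length. The frequency range is the protocol's; windows of 20 and 50 ms are assumptions.

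| SCS frequency | 20 ms window | 50 ms window |
|---|---|---|
| 1 Hz | 0.02 | 0.05 |
| 20 Hz | 0.4 | 1.0 |
| 30 Hz | 0.6 | 1.5 |
| 100 Hz | 2.0 | 5.0 |

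With a 50 ms window, every sweep at 20 Hz or more contains at least one pulse. TMS is given every 4 s. At a whole-number frequency, 4 s holds a whole number of SCS cycles (30 Hz × 4 s = 120). If both clocks are exact, all 20 sweeps share one SCS phase and averaging does not remove the overlap.

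**3. Which way would overlap bias the amplitude?** An illustrative simulation added two signals linearly in a 50 ms window: an MEP drawn as one 12 ms sine cycle starting at 30 ms, and SCS responses of the same shape starting 15 ms after each pulse at 30 Hz. There was no true change. All shapes and sizes are assumptions.

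| SCS response relative to MEP | Apparent MEP ratio, sweeps phase-locked: mean (range) |
|---|---|
| 0.25 | 1.00 (0.88-1.25) |
| 0.5 | 1.02 (0.75-1.50) |
| 1.0 | 1.16 (0.98-2.00) |

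With random phase and the peak-to-peak taken on the averaged sweep, the ratio was 1.00 throughout. Overlap can thus inflate or reduce the amplitude. Facilitation at the motoneuron, by contrast, acts upward.

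**4. How often would a purely spinal shift pass the planned test?** For a paired t-test with n participants, the statistic is noncentral t with n − 1 degrees of freedom and noncentrality δ√n, where δ is the spinal-only shift in SDs of the paired differences. Two-sided alpha of 0.05 is assumed, since Section 8 gives none. n = 12 is the SCI target, 16 is the approximate number of unimpaired participants per protocol type, and 8 is roughly 12 × 0.7 = 8.4, if the 70% completion rate in the sample size section applied to the 12.

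| n | δ = 0.5 | δ = 1.0 | δ at which 80% are significant |
|---|---|---|---|
| 8 | 0.232 | 0.681 | 1.156 |
| 12 | 0.353 | 0.883 | 0.889 |
| 16 | 0.465 | 0.962 | 0.749 |

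These are chances of a significant result with zero corticospinal change, given that a spinal shift of that size exists. The documents do not say how large it is.

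**The case against.** **The protocol's model already includes spinal facilitation.** Aim 1 asks which tract carries the drive through a more excitable cord, not whether SCS acts on cortex or cord. This stands in part: a spinally facilitated MEP is not automatically a wrong answer. But the text labels MEP amplitude as tract excitability, which claims more.

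**The hypothesis is a dissociation.** Enhancement is predicted for tibialis anterior in precision control and not elsewhere, with the opposite pattern for StartReact. A uniform spinal effect, or a constant overlap, does not predict that. This stands. A reader might infer that the SCS-on result is wholly uninterpretable, and the documents do not support that. What remains is a spinal effect that differs by muscle or contraction level, which is plausible because Visit 1 maps recruitment muscle by muscle.

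**The test in Section 8 concerns training.** If it is made with SCS off, concurrent overlap is absent. This stands for overlap, but a spinal after-effect would remain, and Section 8 does not specify the SCS state.

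**The spinal effect is not established for active tasks.** A reader might take the Introduction as settling that SCS acts only below the cortex during movement. It limits that finding to rest and calls the combination with voluntary movement unclear. The ambiguity is open, not decided against the corticospinal reading.

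**Aim 2 has reference conditions.** The visual and soft-sound conditions would share any SCS-evoked EMG, which need not create a startle effect and could dilute one. A reader might infer that Aim 2 is compromised to the same degree. It is less exposed, although onset is still read from EMG.

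**Overlap is not certain.** Section 9.4 equally allows a level set at paresthesia, at which no motor response need occur. This also stands.

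**Conclusion.** The concern holds in a limited form. A rise in MEP amplitude with SCS on, or after SCS training, does not by itself separate corticospinal from spinal facilitation, and with SCS on the sweep may also contain SCS-evoked EMG. The planned task and joint contrasts give partial protection only.

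The size is unknown. It is tempting to attach a percentage inflation to the MEP, but the documents give no response amplitudes, and the illustration shows bias in either direction. The significance probabilities in step 4 are conditional on an assumed spinal shift, alpha and n; they are not estimates of how often this study would err.

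The conclusion rests on the protocol's own account of where SCS acts, on the permitted SCS level and frequency, and on the absence of a written correction. That SCS and the MEP share motoneurons is an inference from the references to spinal networks and graded muscle recruitment. The point concerns analysis and interpretation, and it does not make the study unsound.

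**What to change.** 1. **Correct SCS-on sweeps.** At Visits 4 and 5 record EMG continuously together with SCS pulse times. Average TMS-free, SCS-only segments from the same block and the same task state, aligned to the SCS pulse, and use that average to correct the SCS-on MEP sweeps before measuring amplitude and latency. Report the uncorrected result as a sensitivity analysis, because linear summation is an assumption.
2. **State the SCS condition in Section 8.** Make the before-versus-after training test on SCS-off MEPs, and report the SCS-on versus SCS-off contrast separately.
3. **Visit 5.** Set the EMG-onset threshold in each SCS-on block from that block's pre-target EMG. Test the startle effect relative to the visual and soft-sound conditions within the same SCS state.
4. **Limit the claim.** Describe an MEP rise as a change in net corticospinal-motoneuronal output, level undetermined. Base any tract statement on the pre-specified task-by-muscle dissociation, and state that a muscle-specific spinal effect is not excluded. Section 8 names task and joint but not their combination, so write that contrast out.

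Optional: repeat a short set of the Visit 1 single-pulse responses before and after training at Visits 4 and 5. With an assumed 20 pulses at 4-s spacing this takes 2 × 20 × 4 s = 160 s per visit. It would support statements about spinal after-effects. It should not be a decision rule: measured at rest before and after training, it does not address SCS on versus off or active contraction, and it has no common scale with the MEP.

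The cost is more signal processing, storage of SCS pulse times and a more limited tract claim. No extra participants or visits are needed.
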